Antibodies against rVIII-SingleChain and CHO proteins ^L		X ^K		X		X
FVIII activity level		X ^M				
Virology retention sample			X ^N			X
Distribute and train subject on eDiary			X			
Review subject eDiary and collect at EOS visit				X	X	X
Administer rVIII-SingleChain at clinic^O			X ^O	(X) ^P		
Investigator assessment for treatment efficacy				X		X
Local tolerability (if rVIII-SingleChain administered at clinic)			X	X		
Assign treatment regimen			X ^Q	X ^Q		
Distribute rVIII-SingleChain			X ^R	X ^R		
Collect used / partially used rVIII-SingleChain vials ^S				X		X
Perform drug accountability				X		X
Record date and details of phone contact					X	

Assessments	Visits	Screening (up to 28 days before Visit 1)	Visit 1	Follow-up visits 1 month (± 7 days) after each rVIII-SingleChain dose ^{A,C,E}	Monthly phone calls (± 7 days) if duration between visits is > 1 month ^{B,C,E}	EOS ^D
Confirm that no bleeding episodes have occurred since last visit					X	
Adverse events ^T	←-----On an ongoing basis-----→					
Concomitant medications	←-----On an ongoing basis-----→					

Abbreviations: CD4 = cluster of differentiation 4; CHO = Chinese hamster ovary; eCRF = electronic case report form; ED = exposure day; eDiary = electronic diary; EOS = End of Study; FVIII = coagulation factor VIII; HIV = human immunodeficiency virus; CCI [REDACTED]; PUP = previously untreated patient; rVIII-SingleChain = single chain recombinant coagulation factor VIII.

Notes to the Schedule of Assessments:

- A:** Timing of visits and distribution of rVIII-SingleChain for home treatment depends on when the subject’s bleeding episodes occur. Subjects will return to the site for a follow-up visit 1 month after each rVIII-SingleChain dose. Multiple follow-up visits scheduled to occur within a 10-day time frame may be combined into a single visit (see example in Figure 4). For details, see Section 8.10.2.2.3.
- B:** Monthly phone calls only for subjects whose next bleeding episode does not occur within 1 month after the preceding visit.
- C:** One month is 28 days.
- D:** Inhibitor-negative PUPs will stay in this study until they have achieved 75 EDs; the overall study duration is expected to be up to 6 years. Additional time of up to 3 years in the study may occur for PUPs that develop an inhibitor: CCI [REDACTED]

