3.2.1 Prophylaxis Treatment Regimen

In previous studies, most subjects received prophylaxis treatment with an initial range of 15 to 50 IU/kg rVIII-SingleChain every second day or 2 to 3 times per week. In all study arms, the dose prescribed will be based on the subject's weight at the most recent visit. All subjects will be dosed according to the actual potency printed on the vial label and will be treated by IV injection.

- In Arms 1 and 3 (PTPs), the investigator will determine the rVIII-SingleChain dose and dosing schedule for the subject based upon the subject's PK profile, rVIII-SingleChain

PK data, previous FVIII treatment regimen, bleeding phenotype (if available), and taking into consideration the WFH guidelines [WFH, 2012].

- In **Arm 2 (PUPs)**, the investigator will determine the rVIII-SingleChain dose and dosing schedule at their discretion, taking into consideration the WFH guidelines [WFH, 2012], subject's age and other disease characteristics (eg, bleeding phenotype).

3.2.2 Treatment of Bleeding Episodes in Subjects on Prophylaxis and in Subjects On-Demand Treatment Regimens

In the event of a bleeding episode, subjects will be treated at a dose pre-determined by the investigator based on the type and severity of the bleeding episode. All subjects should treat bleeding episodes with rVIII-SingleChain when they occur, regardless of the assigned treatment regimen. The desired FVIII level for the treatment of a bleeding episode (on-demand treatment) is based on the recommendations of the WFH [WFH, 2012].

All subjects will be dosed according to the actual potency printed on the vial label and will be treated by IV injection.

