3.3 Planned Study Duration

The duration of the study for an individual subject is expected to be approximately 6 years to achieve the following number of EDs with rVIII-SingleChain:

- PTPs in Arm 1 may enroll immediately after participation in previous rVIII-SingleChain studies and continue treatment until achieving at least 100 EDs (including EDs from any previous rVIII-SingleChain study).

- Inhibitor-negative PUPs in Arm 2 will receive treatment in this study until they achieve 75 EDs with rVIII-SingleChain; the overall study duration is expected to be up to 6 years. Additional time of up to 3 years in the study may occur for PUPs that develop an inhibitor:
 - CCI [REDACTED]
 - For inhibitor-positive PUPs who remain in the **main study** who have achieved eradication, the End of Study Visit will occur when they complete the 12-month post eradication follow-up period in the main study. The maximum duration of the inhibitor treatment period is 24 months starting when the dose is initially adjusted to treat the inhibitor, and if no dose adjustment is performed to treat the inhibitor then the duration of inhibitor treatment will be from the date of inhibitor diagnosis.
- PTPs in Arm 3 will receive treatment in this study until they achieve at least 100 EDs with rVIII-SingleChain (excluding EDs from any previous rVIII-SingleChain study that the subject may have participated in).

In all study arms, subjects will complete the study as outlined in [Section 3.1](#) or until the study is terminated by the sponsor.

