## 3 Study Design

### 3.1 Discussion of Study Design

This multicenter, non-randomized, open-label, multiple-arm phase 3 extension study will continue to investigate the safety and efficacy of rVIII-SingleChain in PTPs and PUPs with severe hemophilia A. This study will evaluate the prophylaxis and on-demand treatment of bleeding episodes in at least 200 PTPs who achieve at least 100 EDs as well as in at least 50 PUPs. In Arms 1 and 3 (PTPs), each PTP will stay in this study until they have achieved at least 100 EDs, which overall is expected to take up to 5 years. In Arm 2 (PUPs), each PUP will stay in this study until they have achieved at least 75EDs, which overall is expected to take up to 5 years. A surgical substudy (open to subjects from all study arms) will investigate the use of rVIII-SingleChain in surgery. CCI

[Valentino et al., 2015].

Eligible subjects will be enrolled in 3 Arms, as detailed in [Section 2](#).

This study is designed to collect data on the use of rVIII-SingleChain to assess long-term safety and efficacy beyond the outcome from pre-marketing authorization clinical studies as well as to assess inhibitor development and characterize efficacy and safety of rVIII-SingleChain in PUPs. Inhibitor development is of particular interest for the safety of rVIII-SingleChain.

The preceding lead-in clinical studies, i.e. CSL627\_1001 and CSL627\_3002, are referred to as pivotal studies.

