## 4 Statistical Methodology

### 4.1 Planned Analyses

Statistical programming and analyses will be performed by a Contract Research Organization (PPD [REDACTED]) under the supervision of CSL Behring. Data derivations and manipulations and statistical analyses will be performed using SAS® version 9.2 or higher.

All summaries and analyses will be provided separately for PTPs and PUPs. For the separate presentation of PTPs and PUPs, all summaries and analyses will be presented as a total and by assigned treatment modality (prophylaxis, on-demand) and/or by age group for PTPs: 0 to < 6 years, ≥ 6 to < 12 years, ≥ 12 to < 18 years and ≥ 18 to ≤ 65 years, 0 to <12 years, ≥12 to ≤ 65 years.

All continuous variables will be summarized in terms of the observed sample size, mean, standard deviation, median, minimum, and maximum. Other descriptive statistics (e.g., quartiles, coefficient of variation) may be reported when appropriate. All categorical variables will be summarized using frequency counts and percentages.

Unless otherwise specified, Confidence Intervals (CIs) presented will be two-sided 95%.

Number of subjects screened will be reported. Unless otherwise stated, baseline and demographic characteristics will be summarized for the Safety, Efficacy, Surgery and C [REDACTED] populations. Note: If the Safety and Efficacy populations are equal, only the safety population should be produced and a footnote added regarding the efficacy population.

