## 4.6 Efficacy Analysis

The efficacy endpoints will be summarized and analyzed for the Efficacy population unless otherwise specified. The surgery substudy efficacy data will be summarized for the Surgery population. Efficacy analyses will be performed separately for the PTPs and PUPs and by modality. Efficacy results for the PUPs will be presented by inhibitor status (positive, negative) and overall.

The efficacy evaluation period begins on Treatment Day 1 date in this study and ends at the End of study Visit in this study or the last date of dose, whichever occurs later. Only those treated bleeding episodes and doses which fall within the efficacy evaluation period will count

towards the efficacy evaluation. The summary statistics to be presented are described in [Section 4.1](#).

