### AsBR

AsBR will be derived by inhibitor status and overall as follows:

$$(\text{number of bleeding events}) / (\text{observed treatment period of interest days}) * 365.25.$$

Only bleeding events requiring treatment will be included in the derivation of bleeding rates. The AsBR will be estimated for subjects who complete at least 8 weeks of treatment on the given inhibitor status using the subject's observed data. If the subject does not complete at least 8 weeks of treatment on the given inhibitor status, then the AsBR will be considered missing.

The number of spontaneous bleeding episodes per year based on a Poisson model and associated 95% CI and the number and percentage of subjects with zero bleeding episodes will be presented. In addition, the rate ratio of Prophylaxis modality to On-Demand modality (Prophylaxis- On-Demand) will be presented, along with the associated 95% CI, as obtained by the Poisson model.

Spontaneous bleeding episodes are those classified as 'Non-traumatic' in e-Diary or 'Spontaneous' in the eCRF. Annualized spontaneous bleeding rate will also be summarized for the following subgroup:

- Positive non-inhibitory Anti-Drug Antibodies (ADAs) and negative during the study
- Age based on age in this study: for PTPs: 0 to < 6 years,  $\geq 6$  to < 12 years,  $\geq 12$  to < 18 years and  $\geq 18$  to  $\leq 65$  years, 0 to <12 years,  $\geq 12$  to  $\leq 65$  years.
- Prophylaxis frequency: every second day, 3 times per week, 2 times per week, other regimen.

In these subgroup analyses rate ratio of Prophylaxis modality to On-Demand modality won't be displayed.

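### The percentage of PUPs with zero bleeds is not comparable between modalities, because the 75-ED exit gives unequal, outcome-linked follow-up and no common window is set

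*SAP*

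**What the plan says.** SAP 4.6.1.1 (AsBR) plans, beside the Poisson-based yearly number of spontaneous bleeds and the prophylaxis to on-demand rate ratio, that "the number and percentage of subjects with zero bleeding episodes will be presented". It does not say whether these are spontaneous bleeds only or all bleeds, nor over what period. SAP 4.1 asks for summaries in total and by assigned modality. SAP 4.6 adds: "Efficacy analyses will be performed separately for the PTPs and PUPs and by modality". It also sets the efficacy period as each boy's own time from Day 1 to the End of Study Visit or last dose, whichever is later.

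The length of that period is set by exposure. Protocol 3.3: "Inhibitor-negative PUPs in Arm 2 will receive treatment in this study until they achieve 75 EDs with rVIII-SingleChain". The same section, and the schedules for PUPs assigned to on-demand, expect a study duration of up to 6 years. SAP 3.1 has a different figure: "each PUP will stay in this study until they have achieved at least 75EDs, which overall is expected to take up to 5 years". None of these durations is given by modality.

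An ED is any day with an injection (SAP 4.5.1). Protocol 3.2.1 describes prophylaxis in previous studies as "15 to 50 IU/kg rVIII-SingleChain every second day or 2 to 3 times per week"; for PUPs the schedule is left to the investigator. On-demand boys are dosed as bleeds require (SAP 3.2.2). Switching between modalities is allowed at the investigator's discretion (Protocol 3.2.5).

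**The concern.** The share of subjects with no bleed falls as observation time grows, whatever the treatment. Here observation time is governed by an exit rule that works differently under the two modalities. Prophylaxis doses run towards 75 EDs by the calendar. An on-demand boy who never switches gets there mainly by treating bleeds, apart from the supervised first dose and any preventive, additional or surgical doses. Follow-up is thus unequal and also linked to the outcome. If all treated bleeds count, an on-demand boy who completes 75 EDs with none is close to impossible, while on prophylaxis such a boy is unremarkable. For spontaneous bleeds alone the link is weaker, because traumatic bleeds also add EDs.

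At stake is how a simple percentage is read when it stands next to a primary endpoint in an arm of about 24 boys. A difference between modalities could be taken as efficacy when part or all of it is observation time.

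**Working it through.** The documents give no zero-bleed percentage, bleeding rate or follow-up by modality, so there is no figure to reproduce. The check asks what the percentage would show if bleeding rates were equal.

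**Time to 75 EDs on prophylaxis** (75 divided by EDs per week):
- every second day: 75 / 3.5 = 21.4 weeks
- 3 per week: 75 / 3 = 25 weeks (0.479 years)
- 2 per week: 75 / 2 = 37.5 weeks (0.719 years)

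**Time to 75 EDs on demand, no switch** (75 divided by bleeds per year times EDs per bleed; these inputs are assumptions):
- 12 x 1: 6.25 years
- 12 x 2: 3.1 years
- 24 x 2: 1.6 years
- 36 x 2: 1.0 year

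The 6-year expectation corresponds to 75 / 6 = 12.5 EDs per year.

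**Zero-bleed share at an equal rate.** With Poisson bleeding, P(zero) = exp(-rate x years). The rate is that of the bleeds being counted and is assumed; follow-up is held fixed to isolate its effect.

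| Rate per year | Proph. 25 wk | Proph. 37.5 wk | On demand 1 y | 2 y | 3 y | 6 y |
|---|---|---|---|---|---|---|
| 0.5 | 79% | 70% | 61% | 37% | 22% | 5% |
| 1 | 62% | 49% | 37% | 14% | 5% | 0.2% |
| 2 | 38% | 24% | 14% | 2% | 0.2% | <0.1% |

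At 1 per year, against 2 to 3 years on demand, the gap is 49 - 14 = 35 to 62 - 5 = 57 points with no true difference. At 0.5 per year it is 70 - 37 = 33 to 79 - 22 = 57. If on-demand follow-up is only 1 year, the gap at 1 per year falls to 49 - 37 = 12 to 62 - 37 = 25.

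**Variation between boys.** With gamma-distributed rates, P(zero) = (1 + rate x years / k)^(-k). At mean 1 per year and k = 1: 68% and 58% on prophylaxis at 25 and 37.5 weeks, against 25% at 3 years. The gap narrows to 33-43 points but remains.

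**Switchers.** Assume 1 bleed per year throughout, 24 EDs per year on demand, then 2.5 per week on prophylaxis. A boy starting on prophylaxis takes 75 / 2.5 = 30 weeks, so P(zero) = 56%. A switch at 3 months uses 6 EDs and leaves 69 / 2.5 = 27.6 weeks.
- By assigned modality: on demand 46% against 56%. The gap still favours prophylaxis (25% against 56% for a switch at 12 months).
- By time on each modality: on-demand segment exp(-0.25) = 78%, prophylaxis segment 59%. The direction reverses. For a switch at 6 months the two are about equal (61% and 62%).

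The SAP does not choose between these. Section 4.1 speaks of assigned modality, while the endpoint in Protocol 2.1.2 is a rate during each kind of treatment.

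**Common time point.** At 1 per year, both modalities give exp(-16/52.18) = 74% at 16 weeks and exp(-20/52.18) = 68% at 20 weeks. The artefact is gone.

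**The case against.** **The consequence is limited, and this stands.** The percentage is descriptive and no p values are planned (Protocol 11.3). The Poisson rate and rate ratio use a log-time offset (Protocol 11.3.2.1, SAP 4.13). A reader might infer that the primary AsBR comparison is distorted in the same way; the documents do not support that. Modality is chosen by the investigator, so the groups are not comparable as treatments in any case. Time on study and subject-years are summarised too (SAP 4.5.1). But an offset in a rate model does nothing for a raw percentage in the same display, and follow-up in another table leaves the reader to make the correction.

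**The length of on-demand follow-up is inferred, and this stands.** A reader might infer that it is certainly years. The documents give no duration by modality, frequent bleeding could bring a boy to 75 EDs in about a year, and a switch can end on-demand time within months.

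**The prophylaxis times are minimums, and this stands.** Visits after 25 EDs are 3-monthly, with a month of 28 days, so waiting for the next visit could add up to 12 weeks. At 1 per year the prophylaxis share would then be exp(-37/52.18) = 49% to exp(-49.5/52.18) = 39%. That is lower, but still well above 14%. Weekly prophylaxis would take 75 weeks. Inhibitor-positive PUPs follow other exit rules.

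**Very early withdrawal.** A reader might infer that a boy who leaves in the first week counts as bleed-free. SAP 4.11 excludes subjects with less than 56 days from the bleeding-rate analysis, and the zero-bleed sentence sits in that analysis just after the 8-week rule. The natural reading leaves him out.

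**Conclusion.** The crude zero-bleed percentage, shown by modality, is not comparable between modalities. For boys who stay on one modality at the usual frequencies it favours prophylaxis. The gap is about 33 to 57 points at 0.5 to 1 bleed per year against 2 to 3 years on demand, and 12 to 25 points at 1 per year if on-demand follow-up is only 1 year. These sizes rest on assumed bleeding rates, assumed on-demand follow-up and Poisson counts. The ordering for non-switchers rests only on prophylaxis follow-up being the shorter.

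It would go too far to say that prophylaxis will look better in every case. Switching is free, and if bleeds are counted by time on modality an early switch can reverse the direction. That dependence on an unstated rule is part of the defect. The display by inhibitor status also compares unequal periods, since the 75-ED exit does not govern inhibitor-positive boys; no size is given for it here. The point concerns a companion figure and is worth correcting for that figure alone.

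**What to change.** In SAP 4.6.1.1, for the displays by modality and by inhibitor status, replace the whole-study percentage, or accompany it, with a Kaplan-Meier estimate of remaining free of treated spontaneous bleeds. For the modality display:
- start the clock at the start of the modality, and censor at switch and at end of follow-up;
- read the curve at a time that the shortest prophylaxis course reaches, for example 16-20 weeks;
- show median follow-up and numbers at risk by modality.

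For the display by inhibitor status, start the clock at the start of the status period and censor when it ends. State how switchers are counted and which bleeds count. Apply the same thinking to the percentage of subjects with at least one bleeding episode in SAP 4.6.2.2.

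A percentage restricted to boys observed for 24 weeks should not be used. Every-second-day dosing reaches 75 EDs in 21.4 weeks. Dosing 3 per week gives 72 scheduled EDs by week 24, so three extra bleed-treatment days bring a boy to the exit. The restriction would drop full completers, and preferentially those who bled more.

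The cost is one derivation and one table, with no new data. Intervals will be wide: with an assumed 12 boys per modality and 68% bleed-free, 1.96 x sqrt(0.68 x 0.32 / 12) is about 26 points either side.

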## **4.6.2 Secondary Efficacy Endpoints**

### **4.6.2.1 Annualized Bleeding Rate**

Annualized bleeding rate, as defined in [Section 4.6.1](#), will be derived also by type of bleed, i.e., for total, spontaneous, traumatic, unknown and joint bleeds for PTPs. Only treated bleeds will be considered. The ABR will be estimated for subjects who complete at least 8 weeks of treatment on the given regimen using the subject's observed data. If the subject does not complete at least 8 weeks of treatment on the given regimen, or has no treated bleeding events while on the given regimen, then the ABR will be considered missing.

A summary of ABR will be performed by inhibitor status if the efficacy evaluation period is greater or equal than 8 weeks on the given inhibitor status.

For PUPs, as secondary efficacy endpoints, annualized bleeding rate, as defined in [Section 4.6.1](#), will be presented also for traumatic, unknown and joint bleeds.

Annualized Bleeding Rates will be derived also separately for the **CCI** Population.

A specific analysis will be produced for annualized bleeding rates while subjects are inhibitor positive on PUPs.

Bleeding events details will be listed while subjects are inhibitor positive and for all subjects.

Subjects < 8 weeks of efficacy assessment will be listed.

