11.3.2.1 Primary Efficacy Analysis

For **Arms 1 and 3 (PTPs)**, there is no primary efficacy endpoint.

For **Arm 2 (PUPs)**, the analyses of the primary efficacy endpoints are outlined below:

- The investigator's clinical assessment of hemostatic efficacy for the treatment of **major** bleeding episodes, based on the 4-point ordinal scale (excellent, good, moderate, poor / no response), will be tabulated. The percentage of major bleeding episodes treated successfully (defined as ratings of excellent or good) will be summarized, and reported together with a two-sided 95% CI. To estimate the proportion, the denominator will include all treated bleeding episodes categorized as major. To account for within-subject correlation, generalized linear modeling using SAS' GENMOD procedure will be utilized. The model will contain only the intercept term. The binomial distribution with logit link function will be specified.
- The AsBR will be derived for each subject as follows: ((number of spontaneous bleeding episodes) / (observed treatment period of interest))*365.25. The AsBR will be summarized by regimen (on-demand or prophylaxis) using descriptive statistics. In addition, the number of spontaneous bleeding episodes per year and associated 95% CI will be estimated based on a Poisson model. Generalized linear modeling using SAS' GENMOD procedure will be utilized. The Poisson distribution with log link function, and log_time offset will be specified. The Poisson-based number of spontaneous bleeding episodes per year will be presented by regimen (on-demand or prophylaxis).

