11.3.2.2 Secondary Efficacy Analyses

- In **all study arms**, the analyses of the secondary efficacy endpoints are as follows: The primary efficacy analyses outlined in [Section 11.3.2.1](#) for the AsBR will be repeated for the ABR (traumatic, non-traumatic, and unknown).
- The number of bleeding episodes and the number of treated bleeding episodes will be presented. The number and percentage of bleeding episodes requiring 1, 2, 3, or > 3 injections of rVIII-SingleChain to achieve hemostasis will be tabulated. The total dose per bleeding episode (IU/kg) will be summarized using descriptive statistics.
- The consumption of rVIII-SingleChain, will be derived and expressed in terms of IU/kg per month, IU/kg per year, total IU per injection, per month and per year. Consumption will be summarized using descriptive statistics for on-demand, prophylaxis, and surgery.
- The investigator's clinical assessment of hemostatic efficacy for surgery based on the 4-point ordinal scale will be tabulated.

In **Arms 1 and 3 (PTPs)**, the following analysis will be performed in addition to those above:

- The investigator's clinical assessment of hemostatic efficacy for the treatment of bleeding episodes, based on the 4-point ordinal scale (excellent, good, moderate, poor / no response), will be tabulated by severity (major and non-major). The percentage of bleeding episodes treated successfully, defined as excellent or good) will be summarized and reported together with a two-sided 95% CI. In order to account for within-subject correlation, generalized linear modeling using SAS' GENMOD procedure will be utilized. The model will contain only the intercept term. The binomial distribution with logit link function will be specified.

In **Arm 2 (PUPs)**, the following analysis will be performed in addition to those above:

The investigator's clinical assessment of hemostatic efficacy for the treatment of **non-major** bleeding episodes will be analyzed as described in [Section 11.3.2.1](#) for major bleeding episodes

Details on the analyses for the secondary efficacy endpoints will be provided in the Statistical Analysis Plan (SAP).

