#### 4.1.2 Covid-19 impact

During the course of this study, the global COVID-19 pandemic occurred. All sections with specific Covid-19 analyses described how the impacts of COVID-19 will be reported. PTPs analysis was completed when COVID-19 occurred, and therefore has no impact on PTPs. Specific COVID-19 analyses apply to the following sections:

- [4.3 Disposition of Subjects](#)
- [4.5.10 Concomitant Medication](#)
- [4.7.2 Adverse Events](#)

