## 4.11 Changes in Conduct or Planned Analyses from the Protocol

Section 2.1 and 2.2: In the protocol, incidence of inhibitor formation to FVIII in Arm 2, PUPs is stated that would be performed on at least 50 PUPs. However, this condition has been removed. Given that patients that develop inhibitors may be withdrawn from the study early, they would not necessarily achieve 50 exposure days but we would definitely have to include them in the calculation. Therefore the text was adjusted to ensure the option to properly report the endpoint regardless of these circumstances.

CCI

Section 3.5.3: Efficacy Population definition has been changed removing the exclusive inclusion of subjects who do not have an inhibitor at any time point during the study.

CCI

Section 4.6.1 and 4.6.2.1: In the Annualized Bleeding Rate analysis it has been added that subjects with an efficacy evaluation period less than 8 weeks (56 days) will be excluded from the analysis to exclude bias due to short evaluation period.

Section 4.6.2.2: The analysis of number of infusions of CSL627 required to achieve hemostasis has been added for completeness of analysis.

Section 4.7.1: Incidence of transient inhibitors has been added for completeness of analysis.

Section 4.7.2.1: Analysis of AESIs has been added for completeness of analysis.

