### 4.12.2 Early Withdrawal or Missing data

Refer to the handling of partial dates in [Section 4.12.1](#) and method of analysis for the primary efficacy endpoint in [Section 4.6.1.1](#). Other than these two items, no imputation due to withdrawals or missing data will be applied.

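### SAP 4.6.2.1 treats a previously treated patient with no treated bleeds as having a missing ABR, so observed zeros drop out and the descriptive mean is biased upward

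*SAP*

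**What the plan says.** SAP 4.6.2.1 gives two separate reasons for a missing PTP ABR. One is less than 8 weeks of treatment on the regimen. The other applies if the subject "or has no treated bleeding events while on the given regimen, then the ABR will be considered missing".

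Other parts of the documents bear on this:

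- **Formula.** Protocol 11.3.2.1 states: "The AsBR will be derived for each subject as follows", followed by count divided by days, times 365.25. Protocol 11.3.2.2 repeats that analysis for the ABR in all arms. Neither section excludes subjects without bleeds.
- **Parallel SAP rule.** For the annualized spontaneous bleeding rate (AsBR), SAP 4.6.1.1 has only the duration condition: "If the subject does not complete at least 8 weeks of treatment on the given inhibitor status, then the AsBR will be considered missing". The same section plans to show how many subjects had zero bleeds.
- **Declared change.** SAP 4.11 says that "subjects with an efficacy evaluation period less than 8 weeks (56 days) will be excluded from the analysis". It does not mention a zero-bleed exclusion.
- **Missing data.** SAP 4.12.2, after naming partial dates and the primary efficacy method, adds: "Other than these two items, no imputation due to withdrawals or missing data will be applied".
- **Summaries.** SAP 4.1: "All continuous variables will be summarized in terms of the observed sample size, mean, standard deviation, median, minimum, and maximum".
- **Timing.** SAP 4.1.2 notes that "PTPs analysis was completed when COVID-19 occurred". The SAP change list dates the PTP report to November 2019.

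**The concern.** A PTP followed for at least 8 weeks on a regimen without a treated bleed has an observed ABR of 0. Calling it missing removes the best-responding subjects from the table and leaves a rate conditional on having bled. The minimum total ABR can then never be 0.

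The bias runs against the product, but that does not make it harmless. It depends on the share of bleed-free subjects, so it differs between groups. It should be larger on prophylaxis than on demand, and the SAP presents ABR by modality (4.6) and by anti-drug antibody status (3.5.6). The ordering of two groups can even reverse. Suppose group A has true mean 2 and 50% without bleeds, and group B has true mean 3 and 10% without bleeds. The table would show 2/0.5 = 4.0 for A and 3/0.9 = 3.3 for B.

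**Working it through.** The plan states no ABR, zero-bleed share or power, so there is no figure of its own to reproduce. The check is an identity followed by an illustration.

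**1. Identity.** Let N subjects have at least 8 weeks on a regimen, and let a share p0 have no treated bleeds. Those subjects add 0 to the sum of ABRs. Removing them leaves the sum unchanged and reduces the divisor to N(1 − p0):

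reported mean = true mean / (1 − p0)

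| p0 | Factor | Inflation |
|---|---|---|
| 20% | 1/0.8 = 1.25 | +25% |
| 40% | 1/0.6 = 1.67 | +67% |
| 60% | 1/0.4 = 2.50 | +150% |

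This holds for any mix of follow-up times. Read literally, the trigger is no treated bleeds of any type, so the same subjects leave all five summaries (total, spontaneous, traumatic, unknown, joint), and every mean is inflated by the same factor.

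**2. Smallest value left in the total-ABR table.** One bleed gives 365.25/days: 6.52 per year at 56 days and 1.00 at one year.

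**3. Follow-up range from the documents.** PTPs stay until at least 100 exposure days (protocol 3.3). At the schedules described in protocol 3.2.1, that takes 100 × 2 = 200 days (every second day) to 100/2 = 50 weeks = 350 days (twice weekly). It is shorter in Arm 1, where earlier exposure days count. The synopsis expects up to 5 years.

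**4. Illustrative p0.** Assume negative-binomial counts with mean m = 2 per year and dispersion k = 0.5, 1 or 2, all assumptions. Then p0 = (1 + mT/k)^(−k). For T = 350 days, mT = 2 × 350/365.25 = 1.916. With k = 1, p0 = 1/2.916 = 34.3% and the factor is 1/0.657 = 1.52.

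| Follow-up | p0 at k = 0.5 / 1 / 2 | Inflation, k = 2 to k = 0.5 |
|---|---|---|
| 200 days | 56.0 / 47.7 / 41.8% | +72% to +127% |
| 350 days | 45.5 / 34.3 / 26.1% | +35% to +83% |
| 3 years | 27.7 / 14.3 / 6.2% | +7% to +38% |
| 5 years | 21.8 / 9.1 / 2.8% | +3% to +28% |

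Over m = 1 to 3 per year and the same ranges of T and k, inflation runs from +1% to +223%.

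**5. Median at k = 1.** It moves from 1.0 to 2.1 at 350 days and from 1.4 to 1.6 at 5 years.

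**6. On demand, for contrast.** At an assumed 20 bleeds per year over 5 years, mT = 100. With k = 0.5, p0 = 201^(−0.5) = 7.1%, which gives +8%. With k = 2, p0 = 51^(−2) = 0.04%, which gives 0%.

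**7. Simulation.** With 200 subjects, true mean 2 per year, k = 1, 0.5 to 2 years on regimen and 5,000 replicates, about 31% had no bleeds. The mean was 2.00 with zeros kept and 2.88 under the SAP rule; the median was 1.28 against 2.11. A pooled Poisson rate stayed at 2.00 with zero-bleed subjects kept and rose to 2.77 if they were dropped.

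**The case against.** The best defence is that this is a stray clause, not a rule that was ever applied. SAP 4.11 explains only the 8-week exclusion, 4.6.2.1 lists only subjects with under 8 weeks, and the formula it refers back to gives 0 for a zero count. No PTP results or table shells are in the documents, so nobody can say from them that a published mean is wrong. That is right: the finding concerns what the SAP instructs. It still needs action, because either the rule was applied or the SAP misdescribes the analysis.

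Other points have partial force:

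- **The model.** The sample code in SAP 4.13 models bleed counts with a log-time offset, not the per-subject ABR. A missing ABR therefore does not by itself remove a subject. The Poisson estimates are affected only if a filter is added, and the SAP does not say either way.
- **Visibility of zeros.** SAP 4.6.1.1 plans a zero-bleed count, though for AsBR in previously untreated patients, and 4.6.2.2 plans the share with at least one treated bleed. A reader could roughly correct the mean. If p0 is 50% or more, the corrected median is simply 0. Otherwise, the printed summary does not give it exactly.
- **Weight.** The endpoint is secondary and descriptive, no p-values are planned, and the bias is unfavourable to the product. This limits the severity but does not make the instruction correct.

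**Conclusion.** The concern holds. As written, SAP 4.6.2.1 turns an observed PTP ABR of 0 into a missing value, against the protocol's formula and the SAP's own AsBR rule, and without declaring it. The upward direction is certain once one subject with at least 8 weeks on a regimen has no treated bleed, and the factor 1/(1 − p0) is exact. The size in this trial is unknown because p0 is not given; the percentages by follow-up time rest on assumed rates and dispersions.

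The scope is the PTP descriptive ABR. The primary AsBR in previously untreated patients is untouched by this text, and the Poisson rate and rate ratio are affected only if zero-bleed subjects were also dropped from the model. This should be fixed.

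**What to change.** 1. Delete the zero-bleed condition from SAP 4.6.2.1 and keep the 8-week condition.
2. State that a subject with at least 8 weeks on the regimen and no treated bleeds has ABR 0 for every bleed type, and stays in both the descriptive summaries and the Poisson model.
3. Show the number and percentage with zero treated bleeds by regimen next to the PTP ABR, extending the display already planned for AsBR.
4. Check how the completed PTP programs handled these subjects. If the rule was applied, disclose it and give a corrected PTP ABR table in the final report.

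The cost is one SAP sentence and a program check, plus a rerun and a disclosed corrected table if the rule was used. No new data are needed.
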